6.2.1.1 Other Exploratory Efficacy Analyses

Efficacy Analysis by Component

The single components of the main efficacy variable will be analyzed in a similar way to the main efficacy analysis in section 6.2.1.

Analysis of Death Events

The main efficacy analysis will be repeated for overall death and for its components (Death due to MI, stroke, pulmonary embolism (PE) and systemic embolism (SE), CV death, Non-CV death, Undetermined death, and other reasons).

Pre-Treatment Efficacy Summary

Pre-treatment events between randomization and first dose of study intervention will be listed.

6.2.2 Sensitivity and Supplementary Efficacy Analysis

The exploratory efficacy endpoints will be analyzed using the same method described in Section 6.2.1based on:

- SAF analysis set and TA data scope,
- SAF analysis set and OA data scope,
- FAS analysis set and PA data scope,
- FAS analysis set and TA data scope

6.2.2.1 Stratified Efficacy Analysis

The main efficacy analysis with Cox regression will be repeated incorporating all factors considered in the randomization as stratification factors without interaction terms. if the model converges.

6.2.2.2 Competing Risk Model Analysis

The exploratory variables will be analyzed using a competing risk event model similar to the primary safety endpoint (see section 6.4.1.1). Death due to reasons other than MI, stroke, PE and SE is considered a competing event for the efficacy analysis.

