9.4.6.1 Exploratory efficacy endpoints

The exploratory efficacy endpoints, as assessed by the CIAC, are:

- Incidence of composite and event types of death due to MI, stroke, PE and SE, and non-fatal stroke, non-fatal MI, VTE, major amputation of vascular etiology, and acute limb ischemia
- Incidence of thrombosis of the arterio-venous grafts or fistulas.

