• To evaluate the effect of	Exploratory Efficacy Endpoints
Fesomersen on	• Incidence of the composite and event types of death due to MI, stroke, PE and SE, and stroke,

Table 2-1: Objectives and Endpoints

Objectives	Estimands/Endpoints
thromboembolic events as compared to placebo	 MI, VTE, major amputation of vascular etiology, and acute limb ischemia as assessed by the blinded CIAC Incidence of thrombosis of the arterio-venous
	grafts or fistulas, assessed by the blinded CIAC Other pre-specified Safety Endpoints
• To further evaluate the safety profile of Fesomersen as compared to placebo	• Incidence and severity of AESIs- hepatic enzyme elevation, thrombocytopenia
	• Changes in vital signs and, laboratory assessments
	• Incidence and severity of bleeding of the arterio-venous grafts or fistulas
• To further evaluate the	Other Pre-specified Pharmacodynamic Endpoints
pharmacodynamics of Fesomersen as compared to placebo	• Maximum change in PT, INR and aPTT during the main treatment period
P	• Extent and frequency of clotting on the dialysis filters & circuit
	Changes in d-dimer
	• Thrombin-antithrombin complex (TAT) and Prothrombin fragment 1 + 2 (F1.2)
Other pre-specified	
• To further investigate Fesomersen (e.g. mode-of- action-related effects, safety) and to further investigate pathomechanisms deemed relevant to cardiovascular and renal diseases and associated health problems	• Various biomarkers (e.g. diagnostic, safety, pharmacodynamic, monitoring, or potentially predictive biomarkers)
• To evaluate potential associations between genotypic information and clinical efficacy and / or pharmacodynamics effects	

It is important to note, based on the current expert assessment of the COVID-19 Public Health Emergency, it is to be expected that only a very limited number of patients (<5) will suffer from confirmed COVID-19. Besides, as ESRD patients have to go to the hospital regularly, no increase in missing data is to be expected. For this reason, no intercurrent event linked to the COVID-19 Public Health Emergency is accounted for this study. However, any premature discontinuation will be summarized, and selected analyses will be repeated by confirmed COVID-19 (Yes/No) as reported by the investigator.

3. Study Design

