6.2 Efficacy

6.2.1 Analysis of Exploratory Efficacy Variable(s)

Two exploratory efficacy variables will be considered.

First exploratory efficacy composite endpoint consisting of the following components:

• Death due to MI, ischemic stroke, pulmonary embolism (PE), non-CNS systemic embolism (SE) and undetermined - presumed cardiovascular death

- Stroke (ischemic or undetermined type)
- MI
- Major amputation of vascular etiology
- Acute limb ischemia
- Symptomatic VTE
- Systemic embolism

Second exploratory efficacy endpoint:

• Thrombosis of the arterio-venous grafts or fistulas

The frequency and percentage of participants with an exploratory efficacy event will be reported where the denominator will be total number of participants in each treatment group, within the SAF analysis set and PA data scope. The corresponding exact binomial two-sided 95% confidence interval calculated using Blaker's method will be provided.

Exposure adjusted incidence rate (100 person-years) analysis will be performed by treatment group and overall. In addition, the analysis of the exploratory efficacy variable will be conducted as a descriptive time to first event analysis separately for the three Fesomersen dose groups and placebo, similar to the primary safety analysis (i.e. only treatment emergent efficacy events which occurred during the main treatment period will be considered). Thus, the descriptive analysis focuses on estimating the efficacy under constant BAY2976217 concentration during chronic treatment. This analysis will be based on SAF analysis set and the PA data scope.

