- Treatment: Three dose groups of Fesomersen or placebo on top of standard of care
- Intercurrent events: Of interest is the response to treatment while the participant is
 - o alive (intercurrent event "death") and
 - exposed to study intervention (intercurrent event "premature discontinuation of treatment"),

i.e., both intercurrent events are handled using the same strategy "while alive" or "while on treatment".

Population-level summary:

Death and premature end of exposure to assigned treatment (last administration of assigned treatment plus 28 days) considered a competing event for the safety analysis.

The cumulative incidence function for the event-of-interest as well as the associated competing event(s) together with the corresponding confidence interval will be estimated for each treatment arm using Aalen-Johansen estimators.

The cumulative incidence, i.e. the probability of having a specific event, E, at or before a timepoint, t, $P(T \le t, E = 1)$, will be estimated for time-to-event endpoints by Aalen-Johansen estimators with the competing event.

The difference of the Aalen-Johansen estimators between 40mg Fesomersen and placebo and 80mg Fesomersen and placebo and 120mg Fesomersen and placebo will be presented with a 90% confidence interval.

As the Aalen-Johansen estimator is approximately normal distributed (Aalen, Borgan and Gjessing 2008), the difference of Aalen-Johansen estimators is approximately normal distributed. Thus, the two-sided 90% confidence interval is obtained via:

$$\left[(\widehat{A}J^{TRT}(day) - \widehat{A}J^{Control}(day)) \pm z_{0.95} \sqrt{\sigma^2(\widehat{A}J^{TRT}(day)) + \sigma^2(\widehat{A}J^{Control}(day))} \right]$$

with $\widehat{AJ}^{TRT}(day)$ the Aalen-Johansen estimator for Fesomersen (TRT) at study day, $z_{0.95}$ the 95% quantile of the standard normal distribution and $\sigma^2(\widehat{AJ}^{TRT}(day))$ and $\sigma^2(\widehat{AJ}^{Control}(day))$ are the estimated variances of the Aalen-Johansen estimators at study day, estimated with the Aalen method.

Rates

Cause-specific incidence rates will be calculated for each treatment arm with an 90% confidence interval.

The on-treatment incidence rate will be expressed a "subjects with an event – per 100 participant years". For that the following formula is used:

$$IR_{adj} = \frac{\#Participants with an event}{\sum time under treatment (in days)/(100 * 365.25)}$$

The 90% confidence interval for the exposure-adjusted IR will be computed as

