6.5 Data affected by the war in Ukraine

Data 'affected' by the war in the Ukraine will be assessed during the final Blind Review Meeting and will be documented in the Blind Review Report. As the war started after the primary analysis was completed, it is expected that only data in the post study intervention follow-up period will be affected, the impact of the war is considered to be minor/not substantial on the statistical analysis and on interpretation on the study results. Any missingness due to the war is considered as not related to the outcomes of the study i.e. the missingness is likely noninformative. The EMA guidance "Points to consider on the impact of the war in Ukraine on methodological aspects of ongoing clinical trials" released by the Biostatistics Working Party will be taken into account.

7. Document History and Changes in the Planned Statistical Analysis

Protocol No.: BAY 2976217/21170

- Approval of the SAP version 1.0 dated 25 AUG 2020
- The following changes were made in the SAP Version 2.0 dated 15 DEC 2021:
 - Updated the data scope definitions to cover the follow up and extension periods alone.
 - Updated the concomitant medication period definitions
 - Adapted the safety and efficacy outcome variable sections with the exploratory competing risk analysis including with cause-specific and sub-distribution hazard models
 - \circ Clarified definition of the subgroup of subjects with COVID-19
 - General updates based on new version of the protocol
 - \circ $\;$ Updates to the PK/PD sections based on expert opinion and review
 - o Updated BAY 2976217 to 'Fesomersen'.
 - \circ $\,$ Removed the following subgroups as they do not make sense
 - Medical condition that likely led to RRT
 - Time since the start date for most recent Hemodialysis (including hemodiafiltration)
 - Removed text from section 6.4.3 due to repetition and referenced the text in section 6.4.1.
 - Updated the safety analysis set definition to clarify how subjects who were mis-dosed would be handled
- The following changes were made in the SAP version 3.0 dated 01 FEB 2022:
 - Added undetermined- presumed cardiovascular death to efficacy composite
 - Updated analysis periods and data scopes so they no longer depend on visits
 - Aligned the subgroups across safety and efficacy analyses
- The following changes were made in the SAP version 4.0 dated 31MAY2022:
 - Added section 6.5 relating to the handling of data affected by the war in Ukraine.

8. References

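### SAP 6.2.2.2 still uses the older death list, so a presumed-cardiovascular death is both an event of the efficacy composite and a competing event

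*SAP*

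**What the plan says.** SAP 6.2.1 defines two exploratory efficacy variables. The first is a composite whose fatal component reads "Death due to MI, ischemic stroke, pulmonary embolism (PE), non-CNS systemic embolism (SE) and undetermined - presumed cardiovascular death". The second is "Thrombosis of the arterio-venous grafts or fistulas", which has no fatal component.

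SAP 6.2.2.2 adds a supplementary analysis: "The exploratory variables will be analyzed using a competing risk event model similar to the primary safety endpoint". It then sets the competing event: "Death due to reasons other than MI, stroke, PE and SE is considered a competing event for the efficacy analysis".

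The same four causes are the fatal component in protocol 9.4.6.1 ("Incidence of composite and event types of death due to MI, stroke, PE and SE") and in SAP Table 2-1 ("Incidence of the composite and event types of death due to MI, stroke, PE and SE").

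The safety model that 6.2.2.2 refers to is in SAP 6.4.1.1. There the competing event is "Death and premature end of exposure to assigned treatment", with death not restricted by cause. That section specifies Aalen-Johansen estimates, cause-specific hazard ratios with log-rank tests, and the Fine-Gray model with Gray's test.

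The document history in SAP section 7 records, under version 2.0, that the safety and efficacy "outcome variable sections with the exploratory competing risk analysis" was adapted. The presumed-cardiovascular category was added to the composite in version 3.0. No matching change to the competing-event rule is listed.

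**The concern.** A competing-risk model needs each participant's first event to be of exactly one type. SAP 6.4.1.1 relies on this: its cause-specific hazard is conditional on neither the event of interest nor a competing event having occurred so far. If the same death is assigned to both types, the analysis is not determined for that participant. A programmer who follows 6.2.2.2 removes a component of the composite; one who follows 6.2.1 departs from 6.2.2.2.

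If 6.2.2.2 is followed, every competing-risk output for the composite is affected: the Aalen-Johansen estimates, the cause-specific hazard ratios and log-rank tests, and the Fine-Gray and Gray results. They would then disagree with the event counts in 6.2.1. SAP section 6 produces hazard ratios, log-rank tests and Gray's test only when each compared arm has at least one event. With few events, the coding could therefore decide whether a comparison is produced at all.

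**Working it through.** The plan gives no figure to reproduce. The check is a comparison of definitions, followed by an illustration of size.

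**Definitions side by side**

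| Type of death | Event of the composite (SAP 6.2.1)? | Competing event (SAP 6.2.2.2)? |
|---|---|---|
| MI, ischemic stroke, PE, non-CNS SE | Yes | No |
| Undetermined, presumed cardiovascular | Yes | **Yes** |
| Haemorrhagic stroke, if adjudicated as a stroke death | No | **No** |
| Other causes | No | Yes |

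- Row 2 is the main point: one category lies in both sets. It is not due to any of the four listed causes. SAP 6.2.1.1 also lists undetermined death separately from death due to those four.
- Row 3 is the reverse gap: the death is in neither set. It depends on the adjudication charter, which is not available here.
- For access thrombosis, if the single rule covers both variables, deaths from MI, stroke, PE or SE are neither events nor competing events. The rule can also be read as applying to the composite only.

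The gap in row 3 and the access-thrombosis gap affect only the Aalen-Johansen and Fine-Gray/Gray outputs, because a cause-specific model censors these deaths either way.

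**Size of the main point**

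The planned group size is 72 (SAP 4.7: 72 active per cohort; pooled placebo 3 × 24 = 72). With no censoring, and the death as the participant's first event, each recoded death moves cumulative incidence by 1/72 = 1.39 points.

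For the number of events, protocol 2.3 gives a 25% risk reduction corresponding to an absolute reduction above 3%, so the composite risk is at least about 3%/25% = 12%. No time horizon is stated. Taken as annual (an assumption), the 24-week risk is 1 − (1 − 0.12)^(168/365.25) = 5.71%, and 0.0571 × 72 = 4.1 events per group.

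| Assumed annual risk | 24-week risk | Events per 72 |
|---|---|---|
| 6% | 2.81% | 2.0 |
| 12% | 5.71% | 4.1 |
| 18% | 8.72% | 6.3 |

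Illustration: with 4 events in each of two groups, recoding one event in one group changes that group's incidence from 4/72 = 5.6% to 3/72 = 4.2%. With similar follow-up, the hazard ratio moves from about 1.0 to about 3/4 = 0.75. The documents give no expected number of presumed-cardiovascular deaths.

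**Size of the access-thrombosis point**

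Protocol 2.2.1 gives 40% survival at five years, so the death hazard is −ln(0.4)/5 = 0.183 per year and the 24-week risk is 1 − exp(−0.183 × 168/365.25) = 8.1%. This counts all deaths, so it is an extreme upper bound for the four causes; 2% is taken as a lower value. The access-thrombosis risk of 10% to 25% is assumed.

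With constant hazards over the 24 weeks, let a = −ln(1 − r) for thrombosis risk r and b = −ln(1 − d) for death risk d. The overstatement from censoring the deaths is r − [a/(a + b)] × [1 − exp(−(a + b))].

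| Deaths in 24 weeks | r = 10% | r = 15% | r = 25% |
|---|---|---|---|
| 2% | 0.10 points | 0.15 points | 0.24 points |
| 8.1% | 0.40 points | 0.60 points | 0.98 points |

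**The case against.** The overlap itself is hard to dispute, so the case on the other side is that it matters little.

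- **The effect depends on coding.** If the programmer codes the 6.2.1 components first, nothing changes. This is true, but the SAP does not say to do so, and its explicit rule says the opposite.
- **Most efficacy outputs are untouched.** SAP 6.2.1 also plans a descriptive time-to-first-event analysis on its own definition, as well as counts and rates. This stands and limits the scope.
- **The hazard-ratio illustration is selective.** It recodes one event in one group only. With 3 versus 4 events, the standard error of the log hazard ratio is √(1/3 + 1/4) = 0.76, so the 95% interval is about 0.17 to 3.35 and the shift lies well inside it. The 12% is for an anticipated pivotal-trial composite without the presumed-cardiovascular category. These are fair limits on the illustration. The mismatch in definitions does not depend on it.
- **The smaller points are conditional.** If a fatal haemorrhagic stroke is adjudicated as a bleeding death, 6.2.2.2 already makes it competing. If the rule covers only the composite, access thrombosis could inherit the unrestricted death rule of 6.4.1.1. Both points stand only as conditional.
- **Timing.** SAP 6.5 indicates that the primary analysis is already complete, so recoding would follow the unblinded snapshot. This affects how the change is documented, not whether it is needed.

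**Conclusion.** The concern holds. Two current sections of the SAP assign the same death to incompatible event types, and nothing in either document resolves it. The document history suggests how this arose, but the conflict is visible without it. Following 6.2.2.2 as written miscodes a component of the composite.

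Each affected death is worth about 1.4 percentage points of cumulative incidence in a group of 72, under the no-censoring and first-event assumptions. How many there will be is unknown. The access-thrombosis point is worth at most 0.1 to 1.0 points under the assumed risks, and only on one reading of the text.

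The consequence is confined to a supplementary analysis of exploratory endpoints, in a study whose protocol plans no hypothesis testing. It should be fixed because the error is clear and the remedy is cheap; no primary or secondary result depends on it.

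**What to change.** Replace the competing-event sentence in SAP 6.2.2.2 with a rule for each endpoint: the competing event is any death not itself counted as an event of that endpoint.

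- **Composite:** any death that is not a component in 6.2.1. Presumed-cardiovascular death is then an event only, and haemorrhagic-stroke death is competing.
- **Access thrombosis:** death from any cause.

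Align the composite in SAP Table 2-1 with 6.2.1. While doing so, check the death breakdown in SAP 6.2.1.1, which uses the same four-cause label, and note the difference from protocol 9.4.6.1.

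Because the primary analysis has been run, state which coding it used and document the change as made after that analysis, to apply to the final one.

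The cost is one or two sentences in 6.2.2.2, one table row, an event-coding change and a short entry in the document history. No new data are needed.

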6.2.2.3 Subgroup Analysis

The analysis for the exploratory efficacy variables will be repeated by the following subgroups:

- Age groups
 - <60 years,
 60-75
 >75 years
 - <50yrs
 >=50-<60yrs
 >=60-<65yrs
 >=65-<70yrs
 >=70-<80yrs
 - >=/0-<80yrs
- BMI groups
 - Below 18.5 = underweight; 18.5 to <25.0 = healthy weight; 25.0 to <30.0 = overweight; >= 30.0 = obesity
 - 30 to <35: obesity class 1; 35 to <40: obesity class 2; >=40: obesity class 3
- Gender,
- Previous CV events (MI or stroke or TIA or VTE)
- Previous MACE (MACE is defined as: prior myocardial infarction, prior stroke from the medical history database.)
- History of DM,
- History of Afib,
- Race,
- Time since the start date for renal replacement therapy (<1 year; >=1 year),
- Use of low dose ASA,
- History of COVID-19,

• COVID-19 during the study

The analyses for the subgroups will be repeated for the exploratory endpoints based on SAF analysis set and PA data scope and SAF analysis set and TA data scope. The results will be presented descriptively with forest plots.

6.2.3 Analysis of COVID-19 Patients

Analysis to evaluate the COVID-19 impact on the study exploratory efficacy endpoint will be performed by comparing the descriptive statistics among COVID-19 versus non-COVID-19 patient population. COVID-19 cases will be recorded as adverse events in the eCRF, participants with a documented adverse event of COVID-19 during the study will form the COVID-19 population, all other participants will be included in the non-COVID-19 population. Additional analysis on the COVID-19 will be described in the future SAP revision if needed.

6.3 Pharmacokinetics/Pharmacodynamics.

Plasma and dialysate samples will be collected for measurement of plasma Fesomersen-eq. concentrations and dialysate concentrations of Fesomersen and its metabolites, respectively. PK- and PD- samples will be collected in all participants. A subset of at approximately 24-40 participants will be participating in an alternative PK&PD sampling group with the first dose on a non-dialysis day

There may be some inaccuracies in the actual sampling times compared to planned sampling. These deviations can be relevant for the interpretation of pharmacokinetic and pharmacodynamic data. Accepted time windows are prespecified in the guidance documents for PK and PD validity for study #21170 and will be referenced in the final blind review report. Accepted time windows for the assessment of pharmacokinetic concentrations will be handled analogously.

All valid results will be included in the listings and graphical displays of individual data, which are displayed using actual times. Measurements taken outside the predefined time windows will be flagged by the pharmacokinetic and pharmacodynamic experts to be excluded from the calculation of summary statistics (with respect to planned times) in order to avoid biased results. Samples flagged for other reasons, as defined in respective guidance documents for PK and PD validity for study #21170, will be excluded from statistics accordingly (see also section 4.6).

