8.3.1 Time Period and Frequency for Collecting AE and SAE Information

All AE/SAEs will be collected from the signing of the ICF until the final follow-up visit at the time points specified in the SoA (Section 1.3). Adverse events of special interest (AESI) have to be reported at any time after randomization (treatment, and post-treatment follow-up periods).

All SAEs/AESI will be recorded and reported to the sponsor or designee immediately and under no circumstance should this exceed 24 hours, as indicated in Section 10.3. The investigator will submit any updated SAE data to the sponsor within 24 hours of it being available.

07 JUL 2021 Page: 50 of 90

Investigators are not obligated to actively seek AE or SAE after conclusion of the study participation. However, if the investigator learns of any SAE, including a death, at any time after a participant has been discharged from the study, and he/she considers the event to be reasonably related to the study intervention or study participation, the investigator must promptly notify the sponsor.

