9.4.7 Other analyses

Analysis of COVID-19 Patients

Analysis to evaluate the COVID-19 impact on the study primary safety and exploratory efficacy endpoints will be performed by comparing the descriptive statistics among confirmed COVID-19 versus non-COVID-19 patient population. Additional COVID-19 analysis considerations will be described in the SAP.

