6.4.6 Analysis of COVID-19 Patients

Analysis to evaluate the COVID-19 impact on the study primary safety endpoint will be performed by comparing the descriptive statistics among COVID-19 versus non-COVID-19 patient population. Additional analysis on the COVID-19 will be described in the future SAP revision if needed.

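### The COVID-19 comparison groups participants by any COVID-19 adverse event during the study, with no timing rule, so events that preceded infection count in the COVID-19 group and any effect is diluted

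*SAP*

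**What the plan says.** SAP 6.2.3 sets out to show the impact of COVID-19 on the exploratory efficacy endpoint by "comparing the descriptive statistics among COVID-19 versus non-COVID-19 patient population". COVID-19 cases are recorded as adverse events. On membership it says that "participants with a documented adverse event of COVID-19 during the study will form the COVID-19 population" and that "all other participants will be included in the non-COVID-19 population".

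SAP 6.4.6 plans the same for bleeding: "Analysis to evaluate the COVID-19 impact on the study primary safety endpoint will be performed by comparing the descriptive statistics". It defines no groups of its own, so the definition in 6.2.3 is the only one available. Protocol 9.4.7 describes "comparing the descriptive statistics among confirmed COVID-19 versus non-COVID-19 patient population" and also gives no timing rule.

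The window for recording a COVID-19 adverse event is long. Protocol 8.3.1 states: "All AE/SAEs will be collected from the signing of the ICF until the final follow-up visit". The window for main-analysis outcomes is shorter: under SAP 4.5.2 the primary analysis (PA) scope runs from first dose to the end of the main treatment period, which SAP 4.5.1 puts at 24 weeks.

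SAP 6.2.2.3 lists "COVID-19 during the study" among its subgroups, and SAP 6.4.5 carries the list over to treatment-group comparisons of the primary safety endpoint, in the PA and total treatment (TA) scopes, shown as forest plots. SAP 6.4.5 describes these subgroups as resting on baseline and demographic characteristics.

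**The concern.** An infection cannot influence a bleed that happened before it. Under the SAP's rule, a participant who bleeds in week 3 and is infected in week 50 contributes a bleed to the COVID-19 group. The comparison therefore mixes events before and after infection and cannot separate them, although separating them is what a statement about impact needs. Membership can also change after the outcome window has closed: an infection in follow-up would move an unchanged main-period bleed from one column to the other between the primary and the final analysis.

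The subgroup is a related problem. A split on something that happens after randomisation is not a baseline split, so treatment differences within it are not protected by randomisation. The separate history-of-COVID-19 item in the same list does not have this weakness.

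**Working it through.** The plan states no figure for this comparison, so the check concerns the order of events.

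**Inputs.** Main period 24 weeks, extension up to 24 weeks, follow-up 16 weeks (SAP 4.5.1). Time after first dose is 24 + 16 = 40 weeks without the extension and up to 24 + 24 + 16 = 64 weeks with it. Adding 1 week of screening gives 65, which matches the maximum participation in Protocol 1.1. At the primary analysis, run when the last participant finishes the main period, the latest enrolled have only about 24 weeks observed. Illustrative bleeding proportion 5% and dropout about 15% (SAP 4.7). Fewer than 5 cases expected (SAP 2).

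**Assumption.** The documents give no infection timing. Take infection as uniform over L weeks after first dose and events as uniform over T weeks, independently, with no COVID-19 effect.

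**Share of the COVID-19 group's events that precede infection** = 1 − T/(2L).

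| Outcome window T | Infection window L | Share before infection |
|---|---|---|
| 24 (PA) | 24 | 1 − 12/24 = 50% |
| 24 (PA) | 40 | 1 − 12/40 = 70% |
| 24 (PA) | 64 | 1 − 12/64 = 81% |
| 48 (TA, full extension) | 64 | 1 − 24/64 = 63% |

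With L = 40 or 64, a fraction 1 − 24/40 = 40% or 1 − 24/64 = 63% of infected participants are infected after week 24. All of their main-period events precede infection.

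**Dilution.** If the event rate after infection is R times the rate before it, the ever/never ratio for main-period events is about 1 + (R − 1) × 12/L. For R = 3:
- L = 24: 1 + 2 × 0.5 = 2.0
- L = 40: 1 + 2 × 0.3 = 1.6
- L = 64: 1 + 2 × 0.1875 = 1.4

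A split at onset targets 3.

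**Effect of unequal follow-up.** A simulation with no COVID-19 effect used 5% bleeding and 15% exit per 24 weeks at constant rates, with infection possible to week 64. The infection probability over 64 weeks was set to 4/288, 10% or 20%. The ever/never ratio was 1.07 to 1.09, and about 78% of the COVID-19 group's bleeds preceded infection. Splitting events and person-time at onset gave 0.99 to 1.03.

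**Absolute size.** With 4 cases and 5% bleeding, 4 × 0.05 = 0.2 bleeds are expected in the COVID-19 group, and the chance of at least one is 1 − 0.95⁴ = 19%.

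**The case against.** The strongest reply is that this hardly matters. The comparison is descriptive and supplementary, no hypothesis testing is planned (Protocol 9.1, SAP 4.7), and with fewer than 5 cases the COVID-19 column will be almost empty. SAP 6 calculates hazard ratios and log-rank or Gray's tests only when each compared arm has an event, so formal treatment comparisons in the infected subgroup are unlikely. SAP 6.2.3 and 6.4.6 also leave room for further COVID-19 analysis if needed. All of this stands and sets the priority. It does not repair the rule, and the case count is a forecast, not a cap.

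A second reply is that SAP 4.5.2 defines a data scope as the time window for the data in an analysis, which could be read as limiting COVID-19 adverse events to the same window. The definition in 6.2.3 refers to the whole study, which cuts against that reading. Even if it were accepted, the 24-week row would apply, and half of the events would still precede infection.

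A reader might infer three stronger points that the documents do not support:
- That the comparison can show no COVID-19 effect at all. Events after infection also count, so a large effect would appear, but diluted.
- That the contrast mainly reflects length of follow-up. Under no effect the ratio is only about 1.07 to 1.09.
- That the SAP uses this analysis instead of intercurrent-event handling. SAP 2 omits a COVID-19 intercurrent event because it expects few cases and no increase in missing data; analyses by COVID-19 status are an addition.

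**Conclusion.** The concern holds in this form. The rule in SAP 6.2.3, which 6.4.6 has to borrow, allows exposure to follow outcome. It therefore counts pre-infection bleeds and thrombotic events in the COVID-19 group and dilutes any effect. The share affected is 50% to 81% of the group's main-period events, and about 63% in the TA example. These figures rest entirely on assumed uniform timing, and 6.2.3 and 6.4.6 do not themselves name a data scope.

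The listing of a post-randomisation event as a subgroup for treatment comparisons is also confirmed, and it conflicts with how SAP 6.4.5 describes its own subgroups.

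The consequence is small. Only descriptive, supplementary output is affected, few cases are expected, and the primary bleeding result does not change.

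**What to change.** - **SAP 6.2.3 and 6.4.6:** count events and person-time as COVID-19 only from the start date of the COVID-19 adverse event, within the stated data scope. Count earlier events and time as non-COVID-19. Name the scope in both sections.
- **If cases are as few as expected:** replace the table with a listing of each case showing the COVID-19 onset date and the onset dates of any bleeding or thrombotic events.
- **SAP 6.2.2.3, and 6.4.5 by reference:** delete "COVID-19 during the study" from the forest-plot subgroups and keep the history-of-COVID-19 item.

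Censoring the primary analysis at COVID-19 onset is not needed.

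**Cost:** revised wording and a small amount of reprogramming. Adverse event and outcome dates are already collected. The COVID-19 column will hold very few events. SAP 6.5 indicates that the primary analysis was complete before SAP version 4.0, so a change now should be recorded as made after that analysis.
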